
this purpose, a total of 90 people will be included in the study and three groups will be formed. Combined exercise consisting of aerobic and resistance exercises will be given to the first group, only aerobic exercise will be given to the second group, and the third group will be the control group. The aerobic exercise content is the same in the combined (first group) and isolated aerobic exercise group (second group), for a total of 45 minutes 3 days a week; It will consist of 15 minutes of warming up, 5 minutes of cooling down, 25 minutes of aerobic heart rate (60-80% of the maximum heart rate) at the same metabolic equivalent and with the same energy expenditure, cycling / brisk walking / jogging (low tempo jogging) exercises. Exercise groups will be shown face-to-face in detail before the study, and then the patients will be followed up at regular intervals with appropriate communication tools (phone, mail, etc.). Exercise intensity will be regulated using the perceived effort level (Borg Rating of Perceived Exertion Scale, RPE). During warm-up and cool-down, exercise intensity will be adjusted to be between RPE 11-13, and during aerobic exercise, RPE will be set to be between 14-16. In the combined group (first group), 3 sets x 12 repetitions gradually, after 2 sets x 8 repetitions in the first 2 weeks, using the resistance band (theraband) on other 3 days of the week, every other day; There will be five different resistance exercises(Craniocervical flexion-cervical retraction, reverse flies, shrugs, frontal rise, lateral rise) targeting the neck, upper back and shoulder muscles. Resistance exercise intensity will be adjusted using the OMNI-resistance exercise scale (keeping it between 6 and 8 on the scale). The third group will be asked to continue their normal lives. The exercise will take a total of 12 weeks. After the exercise, an 8-week follow-up period was planned to evaluate the continuation of the exercise effect. Patients will be asked to keep migraine diaries containing the frequency, severity, and duration of migraine attacks for at least 4 weeks before exercise, during 12 weeks of exercise, and during the 8week follow-up period after exercise. The change in the number of days with migraine (in migraine frequency) will be evaluated as a primary outcome measure. Headache severity based on migraine diaries as a secondary measure. At the end of the follow-up period, the surveys will be repeated. Astrand submaximal bicycle ergometer test will be used to measure aerobic capacity. At the end of this process, the effects of combined exercise and isolated aerobic exercise on migraine in patients with chronic migraine will be investigated compared to the control group. In addition, the positive effects of exercise on diseases such as anxiety and depression, which are frequently associated with migraine, and its effects on body aerobic capacity will also be evaluated in the study. Participants will be administered the Hospital Anxiety and Depression Scale(HADS) to compare their anxiety and depression levels, the Migraine Disability Assessment Scale(MIDAS) to assess migrainespecific quality of life, and the International Physical Activity Questionnaire(short form)(IPAQ-short) to compare physical activity status at baseline, at 12 weeks and at the end of the follow-up period Aerobic capacity will be measured indirectly with a bicycle ergometer. This method is the Astrand test, which is a 6-minute cycling test. Pedal resistance is adjusted to be 0.5-1 watt/kg. The speed is adjusted to 60 pedal cycles per minute. Heart rate tracking is measured by a heart rate monitor. The test is terminated when the desired heart rate is reached in the 6th minute. Calculating from the values, aerobic capacity is found

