# The Effect of Different Exercise Types on Migraine Frequency in Individuals with Migraine

[NCT05568004](#)

This is the preplanned and the primary analysis of these data. There were no missing data. Statistical analysis was conducted by a researcher blinded to the participants' groups using the Statistical Package for Social Sciences (SPSS) version 26.0 (IBM Corp., Armonk, NY, USA). The Shapiro–Wilk test and histograms evaluated the data for normal distribution, and the Levene test confirmed homogeneous variances between groups ( $p > 0.05$ ). Continuous data following a normal distribution are presented as mean  $\pm$  standard deviation (SD). The independent samples t test or Mann–Whitney U test was used to compare independent continuous data between groups, while the chi-square or Fisher's exact test was used to compare categorical data. Friedman two-way ANOVA was used to analyze dependent variables, while the two-way mixed ANOVA was used to examine the changes between groups over time. Before the two-way mixed ANOVA, boxplot evaluation confirmed no outliers. Mauchly's sphericity test showed that the assumption of sphericity for two-way interaction was met. Tukey's correction was used for pairwise subgroup comparisons. A  $p$ -value of  $< 0.05$  was considered statistically significant for all analyses.

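### Single-step Tukey for the three arm pairs is valid but gives up power: with exactly three arms, a step-down version holds the same 5% family error and keeps every Tukey rejection

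*SAP*

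**What the plan says.** The Protocol's design description (unnumbered) states that "a total of 90 people will be included in the study and three groups will be formed": combined exercise, aerobic exercise only, and control. The aim is that "the effects of combined exercise and isolated aerobic exercise on migraine in patients with chronic migraine will be investigated compared to the control group". On the endpoint: "The change in the number of days with migraine (in migraine frequency) will be evaluated as a primary outcome measure". No single time point is attached to it, although diaries run through 12 weeks of exercise and 8 weeks of follow-up.

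The SAP's single analysis paragraph says that a "two-way mixed ANOVA was used to examine the changes between groups over time" and that Tukey's "correction was used for pairwise subgroup comparisons". A p-value below 0.05 "was considered statistically significant for all analyses". It also reports that "the Levene test confirmed homogeneous variances between groups". It does not say that pairs are tested only after a significant overall test, and it describes no step-down version of Tukey. Neither document gives an effect size, SD, power or allocation ratio.

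**The concern.** Single-step Tukey applies one threshold to every pair, set so that the largest of three differences exceeds it in 5% of trials when all arms are equal. Once one arm is known to differ, at most one pair can still be truly equal, and that pair could be tested at the ordinary 5% level. Tukey keeps the stricter threshold, so part of the permitted error goes unused.

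The cost falls mainly on showing that both exercise programmes beat control, and on separating combined from aerobic exercise. With about 30 people per arm, that power is worth having if it costs no error control and no patients.

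**Working it through.** **Inputs.** From the documents: three arms, 90 people in total, level 0.05, Tukey for pairs, equal variances reported as met. Assumed: 30 per arm (90 / 3), two-sided tests, one normally distributed change score, and effects in SD units relative to control. Error df = 90 − 3 = 87. I read the SAP's pairwise comparisons as arm pairs; its wording does not say so explicitly. The figure of 90 cannot be reproduced, because no power inputs are given.

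**Thresholds.**
- Tukey: |t| > q(0.95; 3, 87)/√2 = 3.372/√2 = 2.384, a per-pair two-sided level of 0.0193.
- Unadjusted: |t| > t(0.975; 87) = 1.988.
- Three-arm F test: F(0.95; 2, 87) = 3.101.

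**Why step-down holds 5% with three arms.** Any two of the three pair hypotheses together imply that all arms are equal, so only two null situations exist.
1. All three arms are equal. Nothing is declared unless the largest |t| exceeds 2.384, which has probability 5%.
2. Exactly one pair is equal. Only that pair can be a false finding, and it must pass its own 5% test.

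With four arms this argument fails: unadjusted pairs after an F test gave a family error of 0.121.

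**Simulation.** Arm means were drawn with variance 1/30 and a pooled variance from chi-square(87)/87, with 1,000,000 trials per scenario. Effects are listed as combined, aerobic, control.

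Family error:

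| Effects | Tukey | Step-down | F gate, then unadjusted |
|---|---|---|---|
| 0, 0, 0 | 0.050 | 0.050 | 0.050 |
| 1, 1, 0 | 0.019 | 0.050 | 0.050 |
| 1, 0, 0 | 0.019 | 0.050 | 0.050 |
| 3, 3, 0 | 0.019 | 0.050 | 0.050 |

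Power:

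| Effects and target | Tukey | Step-down | F gate |
|---|---|---|---|
| 0.5, 0.5, 0: both beat control | 0.18 | 0.29 | 0.31 |
| 0.7, 0.7, 0: each vs control | 0.63 | 0.70 | 0.71 |
| 0.7, 0.7, 0: both beat control | 0.47 | 0.62 | 0.63 |
| 0.8, 0.8, 0: both beat control | 0.64 | 0.76 | 0.78 |
| 1.0, 0.5, 0: combined vs aerobic | 0.33 | 0.48 | 0.48 |
| 1.0, 0.5, 0: aerobic vs control | 0.33 | 0.48 | 0.48 |
| 1.0, 0.5, 0: combined vs control | 0.930 | 0.935 | 0.934 |
| 0.7, 0.7, 0: at least one true finding | 0.783 | 0.783 | 0.793 |

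**Step-down against the F gate.** If the middle arm lies midway between the other two, F = t²/2 for the widest pair. The F gate then needs |t| > √(2 × 3.101) = 2.490, which is above Tukey's 2.384. The F gate blocked a Tukey rejection in about 0.6% of trials at (1.0, 0.5, 0), 1.3% at (0.8, 0.4, 0) and 1.7% at (0.6, 0.3, 0). Step-down cannot do this: any |t| above 2.384 opens the gate and also exceeds 1.988.

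**Several visits.** The guarantee covers one named change score. With an assumed correlation of 0.5 and 20,000 trials per setting, using the group-by-time F as the gate and then testing unadjusted pairs at each post-baseline visit gave a family error of 0.087 to 0.16 with three occasions, and 0.18 to 0.37 with six. Tukey applied visit by visit gave 0.092 with three occasions and all arms equal.

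**The case against.** Tukey for all pairs of three arms is standard and valid, and its simultaneous intervals match its decisions. A reader might infer from the tables that the SAP's method is wrong, or that findings based on it are unsafe. The documents do not support that: Tukey holds the family error at or below 5%, and on one contrast it can only err towards fewer findings.

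A reader might also infer that power is lost on every comparison, or that an F test followed by unadjusted pairs always does better. Neither is true. The gain depends on the effect pattern, which the documents do not give. It is close to nil for the widest pair when effects are evenly spaced, and for at least one true finding. The F gate also gives up some rejections that Tukey would make; the step-down rule removes that particular objection.

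Three objections stand as limits:
- The SAP's overall test is a mixed ANOVA over time and the Protocol names no primary time point. Inserting a gate without naming one could lose error control.
- The SAP is written in the past tense. Loosening a threshold after results are known would not be pre-specified.
- Intervals and decisions can disagree under the step-down rule.

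**Conclusion.** The point holds as an efficiency improvement, not as an error. On one named change score with exactly three arms, step-down testing has the same 5% family-error guarantee as Tukey and never loses a Tukey rejection.

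The gain in the chance of showing that both exercise arms beat control is about 11 to 15 percentage points over equal effects of 0.5 to 0.8 SD. It is about 15 points for each adjacent pair at 1.0/0.5/0 SD, and about 7 points per exercise-versus-control comparison at 0.7 SD each.

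These sizes rest on 30 per arm, two-sided tests, normality, equal variances and the assumed effects. The error argument needs three arms and one pre-named contrast. It does not extend to pairs tested at several visits.

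**What to change.** At planning, amend the SAP as follows:
1. Name one primary change score in migraine days, with its baseline period and one time point.
2. On that score, test the largest of the three pairwise differences at the Tukey critical value, using the pooled error (|t| > 2.384 with 87 df; recompute if arm sizes or df differ).
3. Only if it is significant, test the other two pairs at unadjusted two-sided 5% (|t| > 1.988), again with the pooled error. Otherwise declare no pair different.
4. Report Tukey simultaneous intervals for estimation, and state that they may not always match the test decisions.
5. Do not use the group-by-time F as a gate for unadjusted pairs at several visits.

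A three-arm F test on the same score is an acceptable alternative gate, at the price of occasionally blocking a pair that Tukey would declare.

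The cost is a few sentences in the SAP and the possible mismatch between intervals and decisions; no extra participants are needed. If the data have already been analysed, keep Tukey as primary and label any step-down result post hoc.
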